During the course of the research, participants will be required to undergo pelvic examinations. This critical procedural step is imperative for the comprehensive evaluation of storage symptoms, aiming to assess the severity and progression of symptoms. The eligibility of research participants is also contingent upon the results derived from these pelvic assessments, ensuring the selection of suitable candidates and the appropriate alignment of the study's objectives with the participants' health profiles. Such meticulous monitoring and assessment not only uphold the integrity of the research but also prioritize the well-being and safety of the participants, reinforcing the ethical and scientific standards governing the study.

Distal urethral cell sampling utilizing a cotton bud will be conducted on the study participants. This non-invasive procedure is anticipated to last approximately three to five seconds and might induce mild discomfort. The sampling process is scheduled for the second, third and fourth visits, primarily to facilitate a comprehensive evaluation of the cellular composition in the distal urethra. Despite the potential discomfort, this meticulous sampling approach is instrumental in gathering crucial data, enabling a deeper understanding of the cellular dynamics and potential changes within the urethral microenvironment over the course of the study.

12. Benefit of the study

This research will be the foundation of knowledge in the future by using objective and subjective assessments results to determine the relationship between low dose vaginal estrogen and storage symptoms of LUTS in postmenopausal women. This study will also increase efficiency in the care of patients with overactive bladder or storage symptoms of LUTS, especially in postmenopausal women, by applying the knowledge gained from this research to provide patients with the best and most appropriate treatment, supported by research outcome and information from this research as well.

13. Ethic consideration

1. Respect for person

Participants will receive all information about the research from an information sheet and will be asked to consent for the research, giving them time to make their own decisions. Then sign it in writing and have the right to refuse to participate in the research at any time. And the information in the research will not be personally identifiable. Instead, it will be assigned a code for research to maintain patient confidentiality.

2. Beneficence/Non-maleficence

Treatment of the participants in this study is standard treatment following steps from a safe and easy method for the patients first, namely receiving advice on lifestyle modification that causes

storage symptoms of LUTS. The intervention in the study has been certified by the Thai FDA, which contains a low dosage and fewer side effects than other drugs used to treat storage symptoms of LUTS.

3. *Justice*

Research has clear inclusion and exclusion criteria. All patients have an equal chance of receiving treatment using a systematic random sampling method. There is no discrimination against any individual resulting in equal benefits.

14. Compensation to research participants in the event of harm or adverse effects on the subject.

The research participants will receive a compensation of 200 THB during the initial visit, which is intended to cover the time and effort invested in the informed consent process and preliminary screening procedures. Following this, during the second visit, once the participant qualifies for enrollment in the trial, an additional compensation of 300 THB will be provided. Subsequently, for both the third and final visits, each participant will be remunerated with 300 THB for every scheduled appointment. These monetary reimbursements not only acknowledge the participants' valuable contribution to the study but also serve to offset any inconveniences or expenses associated with their active involvement in the research. Such compensation strategies are designed to uphold ethical considerations and ensure that the participants' dedication and engagement in the research are duly recognized and appreciated.

Medical care in case of research-related injury or serious event on either an emergency or routine basis will be provided free of charge according to the local standard of care by qualified medical personnel at Ramathibodi Hospital.

15. Conflict of Interests and Budget

No conflict of interest is anticipated, as this research study does not engage private enterprises. The entire budget allocation is projected to be sourced through a funding application submitted to the research grant provided by the Faculty of Medicine, Ramathibodi Hospital, Mahidol University.

16. Reference

1. Tomaszewski J. Featured paper postmenopausal overactive bladder. *Menopausal Review*. 2014;6:313–29.

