To date, no prior investigations have been conducted employing robust methodological approaches to assess the efficacy of 17 β -Estradiol at a dosage of 10 mcg in the treatment of Lower Urinary Tract Symptoms (LUTS) in postmenopausal women, particularly in comparison to a placebo control group. This notable gap in the existing literature underscores the need for a comprehensive and rigorously designed study to investigate the potential therapeutic benefits of 17 β -Estradiol in alleviating LUTS among postmenopausal women, while concurrently establishing its superiority or non-inferiority relative to a placebo intervention. Such an investigation would not only contribute significantly to our understanding of this therapeutic avenue but also provide valuable insights into the management of storage symptoms of LUTS in this specific population.

6. Objective

Primary objective

To determine the efficacy of vaginal 17 β -estradiol treatment in alleviating storage symptoms of LUTS in comparison to placebo.

Secondary objective

- To determine the efficacy of vaginal 17 β -estradiol treatment on urethral maturation index and vaginal pH in comparison to placebo.
- To assess the impact of vaginal 17 β -estradiol treatment on the overall quality of life and the patient's global improvement (PGI) perception.

7. Study Objectives and Study Design Overview

7.1) Study design

The clinical study is a two arm, randomized, double-blind, placebo-controlled trial study of postmenopausal women who suffer from storage symptom of LUTS.

7.2) Population

Postmenopausal women who suffer from storage symptom of LUTS.

7.3) Outcomes

Primary outcome

Storage symptom improvement: will be evaluated using “the International Consultation on Incontinence Questionnaire-Female Lower Urinary Tract Symptoms: ICIQ-FLUTS” (Validated Questionnaire in Thai version)⁽²⁸⁾

It comprises of 5 items, each represent the storage symptoms in the following items;

- Item 2a) nocturia
- Item 3a) urgency
- Item 5a) daytime frequency
- Item 9a) UUI
- Item 11a) SUI

Each item will have 2 parts of sub-categories questions are severity and bothersome.

- In severity categories: the questionnaire has established ranging from 0, denoting the absence of any severity, to 4, indicating the highest level of symptom severity. The cumulative point range across all questionnaire items spans from 0 to 20.

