- In bothersome categories: the questionnaire employ ranging from 0, signifying the absence of any bothersome effect, to 10, representing the utmost degree of symptom bother. The cumulative point range across all questionnaire items encompasses 0 to 50.

The primary outcome interpretation will be predicated on the assessment of storage symptom improvement as follows.

- Improve outcome mean ICIQ-FLUTS post-treatment score less than pre-treatment score.
- Not improve outcome mean ICIQ-FLUTS post-treatment score more than or equal to pre-treatment score.

Secondary outcomes

Subjective assessment

- Assess the impact of urinary storage symptoms on quality of life with reference to social effects by Thai version of International Consultation on Incontinence Questionnaire Urinary Incontinence Quality of Life (ICIQ-LUTSqol), which comprises 20 items. The ranges from 19 to 76, with greater values indicating increased impact on quality of life. ICIQ-LUTSqol is a validated Thai adaptation of King's Health Questionnaire (KHQ).⁽²⁹⁾
- Global Improvement score is evaluated by Thai version of Patient Global Impression of Improvement (PGI-I).⁽³⁰⁾

Objective assessment

- Urethral maturation index (UMI) and maturation value (MV)
- Vaginal pH

7.4) Study procedure

I. First Visit and Recruitment

Participants will be recruited from the urogynecology clinic, menopause clinic, and urology clinic using hospital and public advertisement. An information sheet in Thai language will be provided to health care providers in the designated OPD which can ensure the providers convey the correct study information to potential participant. Participants will only be able to enroll into this study one time.

Informed Consent

Individuals with at least one storage symptom of LUTS presenting to clinics in selected OPD will undergo the informed consent process by principal investigator prior to initiating screening procedures. Consent form in Thai language describing in detail the study procedures will be given to the participant privately in a separate room, and extensive discussion of risks and possible benefits of participation in this study will be provided. Participation will be informed that they may withdraw consent at any time throughout the course of this study.

Screening

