After documentation of informed consent, principal investigator will interview the participant and perform vital signs and physical examination. The urinalysis will be performed by urinalysis test strip before the start of the study. Screening procedures are as follows;

- Pelvic exam
- Pelvic floor muscle strength measured as Brink scale
- POP-Q, Stress test
- Gynecologic ultrasonography with post-void residual volumes (PVR)
- Urinalysis by urinalysis test strip
- Bladder diary: consecutive three-day diary which the time of each micturition and the volume voided, fluid intake, incontinence episodes, episodes of urgency and sensation will be recorded, as might be the activities performed during or immediately preceding the involuntary loss of urine.⁽³¹⁾

After screening procedure, the appointment will be made for the next visit, which is one or two weeks after first visit.

Bladder diary

The study will incorporate the use of essential diagnostic tool, namely the bladder diary, to assess and monitor the outcomes. These assessments will be administered under the careful supervision of the study investigators. These diagnostic tests play a pivotal role in our research, serving as indispensable instruments for evaluating the progression and ultimate success of the treatment interventions.

II. Second Visit and Randomization

At one or two weeks after 1st visit, the following study procedure will be performed;

- Bladder diary interpretation
- ICIQ-FLUTS
- ICIQ-LUTSqol
- Vaginal pH
- Urethral maturation index (UMI)

After evaluating all the data collected during the screening process at the initial visit and combining it with the procedures conducted during the second visit, if the woman does not meet all study inclusion or if the woman has an exclusion criterion, she will not be enrolled into this study. A screening log will be kept of all who were evaluated for participation to document who is and is not enrolled and reason for not enrolling in this study.

Women who meet all the following criteria will participate the study.

Inclusion criteria

1. Presenting with storage phase symptom score more than/equal to 1 evaluated by the ICIQ-FLUTS questionnaire in these items
 - Item 2a) nocturia and/or
 - Item 3a) urgency and/or
 - Item 5a) daytime frequency and/or
 - Item 9a) UUI and/or
 - Item 11a) SUI
2. Being natural or surgical menopause for more than 1 year
3. Absence of urinary tract infection or other identifiable cause

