
Each participant in the study will receive a prescription for the research drug, an adequate supply to cover a 12-week treatment duration. This drug will be uniformly packaged within identical containers, featuring a unique alphanumeric code and detailed usage instructions on the label, thereby avoiding the inclusion of the original medication name. The data analysis will be performed by a statistician who will be the sole individual privy to the allocation of drug A or drug B to their respective groups. It is essential to note that the statistician will remain unaware of which of the two is the active drug and which is the placebo. Additionally, an independent statistician will maintain a sealed randomization list as a contingency. Allocation will be as follows;

Group A

17 β -Estradiol 10 mcg (Femiest® Haupt Pharma Munster GMBH, Muenster, Germany
(ESTRADIOL HEMIHYDRATE 0.0103 milligram)

Group B

Placebo

III. Third Visit

At four weeks after 2nd visit, the following study procedure will be performed;

- Bladder diary, the participant will be reminded to provide a three-day diary prior to schedule visit date.
- ICIQ-FLUTS
- ICIQ-LUTSqol
- PGI-I
- Vaginal pH
- Urethral maturation index (UMI)

Participants will also have clinical evaluation and vital signs measurements evaluated.

Compensation for participants will be provided.

IV. Fourth and Final Visit

At eight weeks after 3rd visit, the following study procedure will be performed;

- Pelvic exam
- Pelvic floor muscle strength measured as Brink scale
- Bladder diary, the participant will be reminded to provide a three-day diary prior to schedule visit date.
- ICIQ-FLUTS
- ICIQ-LUTSqol
- PGI-I
- Vaginal pH
- Urethral maturation index (UMI)

Participants will also have clinical evaluation and vital signs measurements evaluated.

Compensation for participants will be provided. Overall study procedures and flow diagram for study are outlined in topic No.8 Protocol flow chart.

7.5) Sample Preparation, Processing, Handling, Storage

- **Vaginal pH**

To assess pH, a piece of litmus paper (MQuant® pH-indicator stripe) will be placed on the lateral vaginal wall until moistened. A pH of 4.6 or greater indicates vulvovaginal atrophy

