(VVA)⁽³²⁾. According to a preliminary double-blinded study in 67 symptomatic postmenopausal women confirmed that atrophic vaginitis is associated with an increase in the lateral wall vaginal pH and this finding is paralleled by similar changes in pH in the urethra. Also, locally applied vaginal conjugated estrogen cream can normalize the pH in the vagina and urethra. Thus, the testing of the vaginal pH serves both as a surrogate for evaluating urethral pH and as a monitor of compliance with treatment.^(33,34)

- **Urethral maturation index**

Cytohormonal urethral analysis serves as the definitive diagnostic approach for female urogenital atrophy in both clinical and research contexts, primarily owing to the pivotal role of estrogen in facilitating the maturation of the urethral epithelium. The urethral maturation index (UMI) emerges as a promising indicator of the estrogenic status within the body, derived from the ratio assessment of parabasal, intermediate, and superficial cells within a set of 100 cells. The interpretation of UMI values is closely associated with distinctive physiological conditions, wherein a decline in estrogen levels or the onset of menopause is characterized by elevated proportions of parabasal and intermediate cells compared to the reproductive age phase.⁽³⁴⁾

Procedure: We will use wet cotton buds coated with NSS solution to gently swab the distal urethra for cytologic preparation. Smear slides will be prepared for cytologic evaluation by immediately immersing them in 95% alcohol for 24 hours and staining them with a Papanicolaou stain. The urethral epithelial cell will be examined under a microscope and classified into three types: parabasal cells, intermediate cells, and superficial cells by an independent cytologist.⁽³⁵⁾ Two hundred cells were counted at each high-power field which was randomly chosen. Six high-power fields were evaluated and the mean of the cell numbers was calculated.⁽³⁶⁾

Maturation value (MV)⁽³⁷⁾

$$MV = (\% \text{ parabasal cells} \times 0) + (\% \text{ intermediate cells} \times 0.5) + (\% \text{ superficial cells} \times 1.0)$$

Interpretation:^(34,38)

MV = 0-49 = low estrogen effect

MV = 50-64 = moderate estrogen effect

MV = 65-100 = high estrogen effect

- **Urinalysis (dipstick test strip)**

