The procedure commonly incorporates the utilization of Cybow™ 10-urinalysis test strip, which are advanced diagnostic tools designed to analyze multiple urine parameters simultaneously. Initially, a fresh clean-voided midstream urine sample is collected and visually inspected for its

color, clarity, and odor. Subsequently, the Cybow strip is immersed into the urine specimen for a specific duration, enabling the strip's chemical pads to react with the components in the urine. These pads, strategically embedded with reagents, undergo color changes in response to the presence and concentration of specific analytes, including but not limited to pH, protein, glucose, ketones, nitrites, leukocytes, bilirubin, and urobilinogen. The strip is then carefully removed and placed on a flat surface, allowing for accurate color comparison with standardized color charts to quantify the concentration of each parameter. For this research purpose, exclusion of urinary tract infection is imperative for eligible criteria.

Interpretation: In the event of leukocytes displaying a concentration of one plus (1+) or higher, or a positive nitrite result, these findings could be indicative of a urinary tract infection (UTI). It is imperative to note that the presence of a UTI serves as an exclusion criterion during the evaluation process.⁽³⁹⁾

7.6) Statistical analysis

Demographics for enrolled participants will be tabulated and described for each study group including age, ethnicity, occupation etc. All clinical and laboratory data related to objectives will be summarized and compared for each group. Appropriate statistics will be calculated to summarize and compare the range, means, medians, etc., and variability of numerical data. Confidence limits (95%) for means, geometric means and proportions will be calculated. Graphical summaries (e.g., box plots, histograms) will be used to describe and compare distributions of numeric variables. Frequency tables will be used to summarize distributions for discrete data. All clinical and laboratory data related to outcomes will be summarized and compared in the two regimens. T-tests and chi-square tests will be used to assess the statistical significance of differences in two means (possibly log-transformed) or proportions. Descriptive summaries of serious adverse events, subject discontinuations due to adverse events, and potentially clinically significant abnormal values (clinical laboratory or vital signs) will also be provided.

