7.7) Study Subjects

Collect data and publicizing invitations to participate in research “Efficacy of Vaginal 17 β -Estradiol on the Urinary Storage Symptoms in Postmenopausal Women: A Randomized Double-blind, Placebo-controlled Study” in Outpatient departments, Department of Obstetrics & Gynecology, Faculty of Medicine Ramathibodi Hospital

[figure not shown]
7.8) Research site

Outpatient departments, Department of Obstetrics & Gynecology, Faculty of Medicine
Ramathibodi Hospital

7.9) Research plan

Activities	2023					2024												2025		
	8	9	10	11	12	1	2	3	4	5	6	7	8	9	10	11	12	1	2	3
1. Literature review and proposal preparation	■	■	■																	
2. Proposal submission and approval			■	■	■															
3. Data collection and analysis								■	■	■	■	■	■							
4. Manuscript writing and submission																■	■	■	■	

8. Protocol Flow Chart

9. Sample size calculation and inclusion/exclusion criteria

- **Sample size calculation**

The sample size is calculated using two independent population proportions formula.

$$n_1 = \left[\frac{z_{1-\frac{\alpha}{2}} \sqrt{\bar{p}\bar{q} \left(1 + \frac{1}{r}\right)} + z_{1-\beta} \sqrt{p_1 q_1 + \frac{p_2 q_2}{r}}}{\Delta} \right]^2$$

$$\Delta = p_1 - p_2, \quad \bar{p} = \frac{p_1 + p_2 r}{1 + r}, \quad r = \frac{n_2}{n_1}$$

$$q_1 = 1 - p_1, \quad q_2 = 1 - p_2, \quad \bar{q} = 1 - \bar{p}$$

Proportion in group1 (p1) = 0.63

Proportion in group2 (p2) = 0.32

alpha(α) = 0.05 , Beta(β) = 0.2

According to Eriksen PS, Rasmussen H (1991)⁽¹⁴⁾ , after 12 weeks, 62.8% of the women with urological symptoms underwent a change for the better in the estradiol (Vagifem®) group compared to 32.4% in the placebo group. (P < 0.001). With sample size (n) equal to 39 subjects per group and add drop out at rate of 10%, which is equal to 43 subjects per group. The total number of sample size will be 86 subjects.

- **Inclusion criteria**

1. Presenting with storage phase symptom score more than/equal to 1 evaluated by the ICIQ-FLUTS questionnaire in these items

- Item 2a) nocturia and/or
- Item 3a) urgency and/or
- Item 5a) daytime frequency and/or
- Item 9a) UUI and/or
- Item 11a) SUI

2. Being natural or surgical menopause for more than 1 year

3. Absence of urinary tract infection or other identifiable cause

4. Not using hormone replacement therapy or any route of estrogen within 4 weeks

5. Never undergone onabotulinumtoxinA therapy, PTNS, or neuromodulation for OAB treatment

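### Section 7.6 names only unadjusted t-tests and chi-square tests; ANCOVA on the visit-2 value would usually give tighter intervals for four repeated measures, at no extra data cost

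*Combined protocol and SAP*

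**What the plan says.** **Tests.** Section 7.6 (Statistical analysis) is the whole analysis plan. Its only sentence on between-arm testing is "T-tests and chi-square tests will be used to assess the statistical significance of differences in two means (possibly log-transformed) or proportions". It also promises 95% limits for means, geometric means and proportions, but does not mention limits for a difference between arms. It does not say whether a t-test would compare week-12 values or changes from baseline. ANCOVA, regression, mixed models and baseline covariates appear nowhere in the document.

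**Measurements.** Section 7.4, Second Visit and Randomization: "At one or two weeks after 1st visit, the following study procedure will be performed". The list that follows includes ICIQ-FLUTS, ICIQ-LUTSqol, vaginal pH and urethral maturation index, and randomisation is described after it. The same four are repeated at the third visit (week 4) and at the fourth: "At eight weeks after 3rd visit, the following study procedure will be performed", which is week 12. PGI-I appears only at the third and fourth visits.

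**Primary outcome.** Section 7.3 gives ICIQ-FLUTS a severity total ("The cumulative point range across all questionnaire items spans from 0 to 20") and a bother total from 0 to 50. It then reduces the result to improved or not improved: "Not improve outcome mean ICIQ-FLUTS post-treatment score more than or equal to pre-treatment score".

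**Sample size.** Section 9 uses two independent proportions, 0.63 against 0.32, with "alpha(α) = 0.05 , Beta(β) = 0.2": "With sample size (n) equal to 39 subjects per group and add drop out at rate of 10" per cent, giving 43 per group and 86 in total.

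**The concern.** The sample size is set for the binary primary alone. The secondary objectives on maturation, pH and quality of life get whatever precision about 39 evaluable women per arm happens to leave. For each of these measures, and for the ICIQ-FLUTS score itself, the plan already collects a pre-randomisation value. Such a value usually predicts the later one, and a test that ignores it leaves explainable variation in the error term. A test on change uses baseline, but fixes its coefficient at 1 instead of estimating it. In either case the intervals are likely to be wider than the collected data allow. What is at stake is how clearly these outcomes can be read, not whether the tests are correct.

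**Working it through.** **The plan's own figure.** The formula printed in section 9, with 0.63, 0.32, two-sided alpha 0.05 and power 80%, gives 39.54 per arm against the stated 39, so it reproduces to within one woman. Also 39 × 1.1 = 42.9, hence 43 per arm and 86 in total. I use n = 39 per arm below.

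**Inputs not in the documents (assumed).** Pre-post correlation r = 0.3, 0.5, 0.7. SD ratio k (week 12 over baseline) = 0.8, 1, 1.25. Because 7.6 does not name the comparator, both t-tests are shown.

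**Cost of estimating the slope.** With 2n = 78 women, the ANCOVA variance is multiplied by 1 + 1/(2n − 4) = 75/74 = 1.0135.

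**1. Against a t-test on week-12 values.** Variance ratio = (1 − r²) × 1.0135. Interval width scales with its square root.

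| r | 1 − r² | at 39 per arm | interval narrower by |
|---|---|---|---|
| 0.3 | 0.91 | 0.922 | 4% |
| 0.5 | 0.75 | 0.760 | 13% |
| 0.7 | 0.51 | 0.517 | 28% |

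At r = 0.5 this is like having 39/0.75 = 52 women per arm. Break-even is where 1 − r² = 74/75, that is r = √(1/75) = 0.115. At r = 0 the ratio is 1.0135: 1.4% more variance, and √1.0135 = 1.007 in width.

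**2. Against a t-test on change.** Variance ratio = k²(1 − r²)/(1 + k² − 2rk) × 1.0135. Worked case, k = 0.8 and r = 0.3: 0.64 × 0.91/(1.64 − 0.48) = 0.502, times 1.0135 = 0.509.

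| k | r = 0.3 | r = 0.5 | r = 0.7 |
|---|---|---|---|
| 0.8 | 0.509 | 0.579 | 0.636 |
| 1 | 0.659 | 0.760 | 0.861 |
| 1.25 | 0.795 | 0.905 | 0.994 |

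Intervals are narrower by between 1 − √0.994 = 0.3% and 1 − √0.509 = 29%. Denominator minus numerator is (1 − rk)², so the large-sample gain vanishes only when the slope rk equals 1. The 1.0135 factor then again costs 1.4% in variance.

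**3. If treatment breaks the correlation.** Section 7.5 reports that "locally applied vaginal conjugated estrogen cream can normalize the pH in the vagina and urethra". Suppose estradiol does something similar here, so that r = 0 in the treated arm and r₀ in the placebo arm, with equal SDs. The pooled slope is r₀/2, and the variance ratio against week-12 values is (1 − r₀²/4) × 1.0135.

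| r₀ | variance ratio | interval narrower by |
|---|---|---|
| 0.3 | 0.991 | 0.5% |
| 0.5 | 0.950 | 2.5% |
| 0.7 | 0.889 | 5.7% |

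Simulation of 100,000 trials at 39 per arm agrees (0.990, 0.948, 0.889), with ANCOVA type I error close to 5%.

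**The case against.** The strongest reply is that nothing here is an error. Randomisation makes the named tests valid, the only powered test is untouched, and the size of the gain rests on correlations that the documents do not supply. All of that stands. It limits the point to a recommendation about precision. It does not remove it, because the downside is bounded at 1.4% of variance and the baseline is already being collected.

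Two further replies have force. First, the gain may be small where estradiol acts most directly: for pH and maturation it could be only 0.5% to 6% of interval width. Second, 7.6 could be read as a t-test on change, which uses baseline; at k = 1.25 and r = 0.7 ANCOVA then adds almost nothing. Both cases are in the ranges above. It is also fair that the ICIQ-FLUTS score is not listed as an outcome separate from improved/not improved, that it has two totals, and that pH and maturation value have cut-offs which could be analysed as proportions. The added sentence therefore has to name each variable.

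A reader might infer that the unadjusted tests are biased, or that the primary analysis must be adjusted too. The documents support neither. Improvement is already defined against each woman's own baseline, and chi-square matches the two-proportion calculation in section 9. In simulations at 39 per arm under assumed score distributions, a baseline-adjusted linear model for the binary outcome had a variance ratio of about 0.72 to 1.01, and its power could fall slightly below that of chi-square. That gain is too uncertain to recommend.

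**Conclusion.** The point holds as a matter of efficiency. Section 7.6 names no baseline-adjusted analysis for measures taken before randomisation and again at week 12, and ANCOVA would usually narrow their intervals. The size rests on an assumed correlation of 0.3 to 0.7, an SD ratio of 0.8 to 1.25 and 39 women per arm: about 4% to 28% against week-12 values, about 0.3% to 29% against change, and about 0.5% to 6% against week-12 values for pH and maturation if treatment removes the correlation in its own arm. Against week-12 values, ANCOVA loses only if the correlation is below about 0.12. The upper ends of these ranges should not be read as the expected gain, since the documents give nothing from which to estimate it. The change is worth making before unblinding, partly because it also settles whether week-12 values or changes are compared.

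**What to change.** Add to 7.6: the week-12 ICIQ-FLUTS severity total (0 to 20), ICIQ-LUTSqol score, vaginal pH and urethral maturation value will each be compared between arms by ANCOVA, with arm and the visit-2 value of the same measure as terms (the visit-2 value transformed in the same way if the outcome is log-transformed), reporting the adjusted between-arm difference with its 95% CI.

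Use the maturation value, a single number, not the three-part cell index. Keep chi-square for the binary primary and add no adjusted version of it. PGI-I has no baseline and needs no change.

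Cost: one sentence and a standard regression command. No extra data, visits or participants are needed, and the sample size does not change.
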